## 10 Quality of life analysis

Patient questionnaires analysis will be conducted on *the core population (CP)*, *the target population (TP)* and *the core population with sufficient follow-up data (CPSFU)*.

The results will be reported overall and for scheduled treatment combination ( $\pm$  RBV) and duration (12 or 24 weeks) groups.

Tables with descriptive statistics for baseline and post-baseline time points will be prepared for each questionnaire results in accordance with section 7.1. Confidence intervals will be presented according the section 7.2. All corresponding listings will be presented. Additional listings for *the non-core population (NCP)* will be created.

### 10.1 EQ-5D-5L

The following EQ-5D-5L parameters will be analyzed:

- the EQ-5D-5L descriptive system dimensions:
  - mobility;
  - self-care;
  - usual activities;
  - pain/discomfort;
  - anxiety/depression;
- the EQ VAS;
- the EQ-5D-5L index value.

Descriptive statistics for each of the 5 dimensions comprising the EQ-5D descriptive system will be reported in two ways:

- using a division into 5 levels of perceived problems:
  - no problems (level 1);
  - slight problems (level 2);
  - moderate problems (level 3);
  - severe problems (level 4);
  - extreme problems (level 5);
- using a division into 2 levels of perceived problems:
  - no problems;
  - problems.

The EQ-5D-5L index value will be calculated by applying US weights. In case of missing items no index value will be calculated.

Summary tables for the EQ VAS and the EQ-5D-5L index value will show descriptive statistics for time point values and changes from baseline value.

Also a graphical representation of the EQ-5D-5L results will be presented.

In addition the models of *analysis of covariance* (ANCOVA) will be applied for EoT and SVR12 time points to investigate the effect of the different ABBVIE REGIMENS ( $\pm$  RBV and duration) on EQ-5D-5L endpoints (EQ VAS and EQ-5D-5L index score).

For each time point (EoT and SVR12) a separate model will be built. The EQ-5D-5L results for each time point will be used as dependent variables. Treatment regimen group will be used as factor. Baseline values will be used as covariates. *Independent-samples t-test* will be

used for post-hoc comparisons. If there are more than two treatment groups, *no adjustment* will be used to counteract the problem of multiple comparisons due to the explanatory study nature.

ANCOVA results will be prepared using SAS PROC MIXED. Studentized residuals figures will be presented for each ANCOVA analyses.

As a supporting analysis the comparisons using Mann-Whitney U-test will be performed.

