9.7.5 Patient Questionnaires

The EQ-5D-5L is a health state utility instrument that evaluates preference for health status (utility). The EQ-5D-5L comprises 5 dimensions (mobility, self-care, usual activities, pain/discomfort, anxiety/depression) each of which are rated on 5 levels of

Confidential Information

No use or disclose outside AbbVie is permitted without prior written authorization from AbbVie

Version 3.0 (22 Apr 2015) – country v 1.0 dated 26.06.2015

Page 37 of 61

severity (1: indicating no problem, 2: indicating slight problems, 3: indicating moderate problems, 4: indicating severe problems, 5: indicating extreme problems), and a separate VAS.

Patients' responses to the EQ-5D-5L will be combined into a unique health state using a 5-digit code with one digit from each of the 5 dimensions representing the level of severity. These EQ-5D-5L states will be converted into a single preference-weighted health utility index score by applying country-specific weights (if available) or US weights (if not available).

No imputation will be performed for missing items, and in case of missing items no index score will be calculated.

A summary table will show descriptive statistics (n, mean, median, SD, minimum and maximum) of the index score values and for the VAS values for baseline and the post-baseline time points, as well as changes from baseline both for the index score values and for the VAS values. In addition analysis of covariance (ANCOVA) will be applied to investigate the effect of the different ABBVIE REGIMENS (\pm RBV and duration) on EQ-5D-5L endpoints using the corresponding EQ-5D-5L baseline values as covariates.

Assessments of work productivity and activity impairment as assessed by the WPAI Hep C v2.0 will be evaluated according to the WPAI-SHP scoring manual. The WPAI yields four types of scores, the results of which will be presented as percentage of impairment from 0 to 100. Higher percentages indicate greater impairment:

1. % absenteeism: percentage of work time missed due to hepatitis C
2. % presenteeism: percentage of impairment while working due to hepatitis C
3. % TWP: percentage of overall work impairment due to hepatitis C
4. % TAI: percentage of general (non-work) activity impairment due to hepatitis C

The WPAI Hep C v2.0 consists of 6 questions aimed at the following targets:

- Q1. currently employed (yes, no)
- Q2. hours missed due to hepatitis C in the last seven days

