9.7.6 PSP and PAM

The contribution of the patient support program (PSP) to disease control, treatment continuation over time, patient satisfaction and PSP utilization will be analyzed using descriptive and exploratory statistical methods. Appropriate frequency tables will summarize all corresponding variables of the PSP questionnaire (see ANNEX 4 and 5) over time stratified by ABBVIE REGIMEN arms. In addition, multiple logistic regression (MLR) analysis will be performed to investigate the association between the use of the PSP and the patient satisfaction variables of the PSP questionnaire with the probability of treatment completion. These MLRs will be performed similar to the MLRs for SVR12 (see Section 9.7.3.3. Additional details will be specified in the SAP).

The Patient Activation Measure (PAM) 13 item scale is a measure used to assess the patient knowledge, skill, and confidence for self-management. Each of the 13 items can be answered with one of four possible response options, which are “disagree strongly” (1), “disagree” (2), “agree” (3), “agree strongly” (4).

Based on responses to the 13-item measure, the score is calculated by adding up the raw scores (range of the sum: 13 – 52) and mapping up the value onto a scale of 0–100 indicating strength of agreement with the 13 items $(100 * (\text{sum} - 13) / (52 - 13))$. The final score can be assigned to one of the four levels of activation. A higher score indicates that the patient is likely to participate more actively in health care processes and takes more responsibility for his or her health.

In case of missing item values, the mean value of the available items will be used for replacement. However, if there are less than nine items answered, no summary score will be calculated.

A summary table will show descriptive statistics (n, mean, median, SD, minimum and maximum) for the summary score at baseline and the post-baseline time points, as well as changes from baseline. In addition analysis of covariance (ANCOVA) will be applied to investigate the effect of the different ABBVIE REGIMENS (\pm RBV and duration) on the

Confidential Information

No use or disclose outside AbbVie is permitted without prior written authorization from AbbVie
Version 3.0 (22 Apr 2015) – country v 1.0 dated 26.06.2015 Page 39 of 61

summary score using the corresponding baseline value as covariates. Further details will be specified in the SAP.

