### **10.4 PAM-13**

The following PAM-13 parameters will be analyzed:

- items of scale;
- PAM 13 score;
- levels of activation.

The 13 items have four possible response options with scores from 1 to 4 (1 – strongly disagree, 2 – disagree, 3 – agree, 4 – strongly agree) and an additional “not applicable” option.

PAM 13 score is a value on scale from 0 to 100. This score will be converted to one of the four levels of activation:

- disengaged and overwhelmed (1);
- becoming aware, but still struggling (2);
- taking action (3);
- maintaining behaviors and pushing further (4).

The PAM 13 score and the level of activation will be obtained using Excel file “PAM 13 Scoring Spreadsheet 2015.xlsm” which was received from the Sponsor’s company.

In case of missing item values, the value for replacement will be determined as the integer part of the available items mean value (i.e. worst-case value imputation).

However, if there are less than ten items answered, no summary score will be calculated (the answers of this patient will be reported only in tables with descriptive statistics for items of scales).

Summary tables for the PAM 13 score will show descriptive statistics for time point values and changes from baseline value. Summary tables for the levels of activation will show descriptive statistics for time point values.

---

 Parameter “Will patient participate / or is patient participating in the AbbVie patient support program (PSP)?” from eCRF form “DEMOGRAPHICS”.

In addition the models of analysis of covariance (ANCOVA) will be applied for EoT time point to investigate the effect of the different ABBVIE REGIMENS ( $\pm$  RBV and duration) on the PAM 13 score using the corresponding baseline value as covariates.

The PAM 13 result for EoT time point will be used as dependent variable. Treatment regimen group will be used as factor. Baseline values will be used as covariates. Independent-samples t-test will be used for post-hoc comparisons. If there are more than two treatment groups, the no adjustment will be used to counteract the problem of multiple comparisons due to explanatory study nature. The obtained p-values of significance levels will be presented before and after the application of the correction.

ANCOVA results will be prepared using SAS PROC MIXED. Studentized residuals figures will be presented for each ANCOVA analyses.

As a supporting analysis the comparisons using Mann-Whitney U-test will be performed.

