**Table 3.6.2.1 EQ-5D-5L, VAS, ANCOVA results**  
The core population  
Page X of X

| Time point | Regimen group / Parameter         | Result at time-point_____ |         |                 | Difference between Regimen groups_____ |                 |                            |
|------------|-----------------------------------|---------------------------|---------|-----------------|--|-----------------|----------------------------|
|            |                                   | n                         | LS mean | 95% CI          | LS mean                                | 95% CI          | p-value                    |
| EoT        | Regimen group 1                   | XX                        | XX.XX   | (XX.XX - XX.XX) | XX.XX                                  | (XX.XX - XX.XX) | X.XXXX
X.XXXX
X.XXXX |
|            | Regimen group 2                   | XX                        | XX.XX   | (XX.XX - XX.XX) | XX.XX                                  | (XX.XX - XX.XX) |                            |
|            | ...                               |                           |         |                 |  |                 |                            |
|            | Covariate (baseline value)        |                           |         |                 |  |                 | X.XXXX                     |
|            | Fixed factor 1                    |                           |         |                 |  |                 | X.XXXX
X.XXXX
X.XXXX |
|            | ...                               |                           |         |                 |  |                 |                            |
|            | Comparison:                       |                           |         |                 |  |                 | X.XXXX                     |
|            | Regimen group 1 - Regimen group 2 |                           |         |                 |  |                 |                            |
|            | ...                               |                           |         |                 |  |                 |                            |
| SVR12      | Regimen group 1                   | XX                        | XX.XX   | (XX.XX - XX.XX) | XX.XX                                  | (XX.XX - XX.XX) | X.XXXX
X.XXXX
X.XXXX |

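### SAP 10.1 and 10.4 name an independent-samples t-test for post-hoc regimen comparisons, so the pairwise p-value can disagree with the baseline-adjusted LS-mean difference beside it

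*SAP*

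**What the plan says.** SAP 10.1 builds a separate ANCOVA at EoT and at SVR12 for EQ VAS and for the EQ-5D-5L index. The time-point value is the outcome, regimen group is the factor, and "Baseline values will be used as covariates". The next sentence gives the post-hoc test as "Independent-samples t-test", without multiplicity adjustment. The section then says "ANCOVA results will be prepared using SAS PROC MIXED" and adds a Mann-Whitney comparison as supporting analysis.

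SAP 10.4 has the same structure for the PAM-13 score at EoT: "Independent-samples t-test will be used for post-hoc comparisons".

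The table shells 3.6.2.1 (EQ VAS, with the index value to follow the same layout) and 3.12.15 (PAM-13) are titled as ANCOVA results. They report LS means with 95% CI, a block headed "Difference between Regimen groups", p-values for the baseline covariate and for the fixed factor, and a comparison row, "Regimen group 1 - Regimen group 2", with its own p-value. A footnote to each table defines the LS mean as covariate-adjusted. Neither shell says which test supplies the p-value in the comparison row.

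The Protocol names only the adjusted analysis: ANCOVA "using the corresponding EQ-5D-5L baseline values as covariates" (9.7.5), and for PAM-13 ANCOVA on the "summary score using the corresponding baseline value as covariates" (9.7.6). SAP 16 states that the methods agree with the Protocol and does not list the t-test as a change.

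**The concern.** An independent-samples t-test has no covariate. It compares raw group means at follow-up, whereas the LS-mean difference compares means at a common baseline value. If the text is programmed as written, one table can carry a baseline-adjusted estimate and interval next to a p-value that answers another question.

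This matters more here than in a randomised trial. Protocol 9.1 leaves the regimen to the physician. Protocol 9.7.2 says that subtype, fibrosis status and prior treatment are relevant to the scheduled combination and duration. SAP 6 excludes cirrhotic genotype 1a patients not receiving ribavirin from the core population, which ties ribavirin use to cirrhosis. Different baseline quality of life between regimen groups is therefore plausible, although the documents give no baseline questionnaire data.

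**Working it through.** **The plan's own figures.** No sample size, SD, effect size or power is stated for the questionnaire comparisons. The only design figure is for SVR12: 158 evaluable patients at 90%, exact 95% CI 84.2–94.2%. It reproduces: Clopper-Pearson with 0.90 × 158 = 142.2 responders gives 84.23–94.20%, width 9.97%. It is used below only as a total N.

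**What each method estimates.** With a common within-group slope b of follow-up on baseline:

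raw mean difference = LS-mean difference + b × (difference in baseline means).

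The two agree in expectation only if b or the baseline difference is zero.

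**Example in SD units (assumed values).** LS-mean difference +0.30, b = 0.7, and the benefiting group starting 0.5 SD lower: 0.30 + 0.7 × (−0.5) = −0.05. The raw difference has the opposite sign to the adjusted one.

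**Simulation.** 20,000 data sets per scenario compared the pooled two-sample t-test on follow-up values with the baseline-adjusted ANCOVA contrast, both two-sided at 5% (SAP 7.2).

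Assumptions not in the documents:
- all 158 patients contribute, split 79/79 or 40/118
- baseline–follow-up correlation 0.3, 0.5 or 0.7
- baseline difference 0, 0.25 or 0.5 SD
- adjusted difference 0 or 0.3 SD, with any imbalance placing the first group (79 or 40 patients) lower at baseline

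| Scenario | Quantity | 79/79 | 40/118 |
|---|---|---|---|
| No adjusted difference, baseline difference 0.25–0.5 SD | t-test rejects | 7.5–59% | 6.8–47% |
| | ANCOVA rejects | about 5% | about 5% |
| Adjusted difference 0.3 SD, baseline difference 0.25–0.5 SD | t-test rejects | 6–29% | 6–23% |
| | ANCOVA rejects | 48–74% | 38–62% |
| | verdicts differ | 21–75% | 17–63% |
| No baseline difference, adjusted difference 0 | verdicts differ | 3–7% | 3–7% |
| No baseline difference, adjusted difference 0.3 SD | verdicts differ | 10–34% | 10–32% |

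At correlation 0.7, baseline difference 0.5 SD and adjusted difference 0.3 SD, the raw and LS-mean differences had opposite signs in about 60% of data sets (62% and 59% for the two splits).

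The t-test rejections in the first row are not errors for its own null hypothesis, because the raw means really do differ. They are misleading only when printed as the p-value for an LS-mean difference.

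**The case against.** The strongest reply is that the authors meant the t-tests of LS-mean differences that PROC MIXED can produce. The t-test sentence directly follows the covariate sentence, the shells are laid out for LS-mean differences, and the ANCOVA shells contain no raw-score t-test output. This is a fair reading, although the extracted table layout is not conclusive. It does not rescue the wording: the test named is a different procedure, and a programmer following the text would run it.

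A reader might infer that the SAP throws away the baseline adjustment altogether. It does not. On either reading, the shells report the adjusted difference, its CI and an adjusted p-value for the regimen factor. With exactly two groups, that factor p-value is already the adjusted pairwise p-value. With more than two, which SAP 10.1 allows for, it is an overall test, and the comparison rows are the only pairwise p-values.

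A reader might also infer that the reported intervals will be wider, or put a VAS-point figure on the bias. Neither is supported. The interval in the shells is the LS-mean interval, and the documents give no imbalance, slope, SD or regimen group size.

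Nor does the supporting Mann-Whitney test call for a switch to change from baseline. Change leaves (b − 1) × the baseline difference, so it over-corrects whenever b is below 1, and the SAP already labels that test supporting.

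Finally, the SAP cites Protocol version 4.0 (11 July 2017), while the protocol supplied is version 3.0, country version 1.0. The departure from the Protocol is established only against the supplied version.

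**Conclusion.** The point holds as a fault in specification. The test named in SAP 10.1 and 10.4 does not estimate the quantity tabulated in the shells, and it is not in the Protocol as supplied. Followed literally, it can give a pairwise p-value that conflicts with the LS-mean difference and CI in the same table. The identity above shows the mechanism without further assumption beyond a common slope. The simulated frequencies rest on assumed correlations, imbalances, effect and splits and are illustrative, not predictions for this study.

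The impact is limited to exploratory secondary patient-reported outcome comparisons. The primary SVR12 analysis does not depend on them. Adjusting for one baseline score also does not remove confounding by indication, so even the corrected comparison is not a causal regimen effect.

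**What to change.** In SAP 10.1 and 10.4, replace the t-test sentence with a statement that pairwise regimen comparisons are the baseline-adjusted LS-mean differences, with 95% CI and p-value, from the same PROC MIXED model (LSMEANS with the DIFF option). Delete the independent-samples t-test, or keep it as a separately labelled unadjusted sensitivity analysis outside the ANCOVA tables. Add a footnote to Tables 3.6.2.1 and 3.12.15 naming the model contrast as the source of the comparison-row p-value. Describe the results as differences between label-defined groups. If the unadjusted t-test is kept, list it in SAP 16.

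The cost is a sentence in each section and a footnote in each shell. No new data or software procedure is needed. SAP 2 allows revision before database soft lock; after that, the departure should be explained in the CSR.

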### 10.2 WPAI

Assessments of work productivity and activity impairment as assessed by the WPAI Hepatitis C will be evaluated according to the WPAI:SHP v2.0 scoring manual.

The following WPAI parameters will be analyzed:

- the WPAI Hep C v2.0 question answers;
- the WPAI:SHP scores.

The WPAI Hep C v2.0 consists of six questions:

- currently employed (Q1);
- hours missed due to hepatitis C in the last seven days (Q2);
- hours missed due to other reasons in the last seven days (Q3);
- hours actually worked in the last seven days (Q4);
- degree hepatitis C affected productivity while working (Q5);
- degree hepatitis C affected regular activities (Q6).

If any of the items Q1-Q6 will be presented as interval it will be replace by mean value for calculations.

WPAI outcomes are expressed as impairment percentages, with higher numbers indicating greater impairment and less productivity, i.e. worse outcomes.

The following four WPAI:SHP scores will be calculated and analyzed:

- absenteeism as percentage of work time missed due to hepatitis C:

$$100 \times \frac{Q_2}{Q_2+Q_4};$$

- presenteeism as percentage of impairment while working due to hepatitis C):

$$100 \times \frac{Q_5}{10};$$

- TWP (percentage of overall work impairment due to hepatitis C):

$$100 \times \frac{Q_2}{Q_2+Q_4} + \frac{Q_4}{Q_2+Q_4} \times \frac{Q_5}{10};$$

- TAI (percentage of general (non-work) activity impairment due to hepatitis C):

$$100 \times \frac{Q_6}{10}.$$

A score will be set to missing if one or more of the items Q1-Q6 that are needed for the calculation of the score is missing.

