- Q3. hours missed due to other reasons in the last seven days
- Q4. hours actually worked in the last seven days
- Q5. degree hepatitis C affected productivity while working
- Q6. degree hepatitis C affected regular activities

The four scores will be derived as follows:

1. % absenteeism: $100 \times Q2 / (Q2 + Q4)$
2. % presenteeism: $100 \times Q5 / 10$

Confidential Information

No use or disclose outside AbbVie is permitted without prior written authorization from AbbVie

Version 3.0 (22 Apr 2015) – country v 1.0 dated 26.06.2015

Page 38 of 61

3. % TWP: $100 * \{Q2/(Q2+Q4) + [Q4/(Q2+Q4)] * Q5/10\}$
4. % TAI: $100 * Q6/10$

A score will be set to missing if one or more of the items Q1-Q6 that are needed for the calculation of the score are missing. No imputation will be performed for missing items.

The summary table will present the absolute and relative frequencies of employed and unemployed patients and descriptive statistics for the four scores. Further details of the analysis will be specified in the SAP.

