### **16 Summary of changes to the Protocol**

The analyses methods in this SAP is fully consistent with the clinical study Protocol. The MLR analysis for the PSP results will not be performed due to lack of main predictor variability (the fact of the PSP usage is always “Yes”).

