**P15-743 (HCV RWE)\_ STATISTICAL ANALYSIS PLAN \_ final 2.0 \_ 02 Feb 2018**

Similar to table 3.8.2, the following table will be constructed:

- Table 3.8.3 WPAI Hep C v2.0. Q3 - Hours missed from work because of other reason
    - Table 3.8.4 WPAI Hep C v2.0. Q4 - Hours missed of actually work
    - Table 3.8.5 WPAI Hep C v2.0. Q5 - Hepatitis C effect on productivity
  - Table 3.8.6 WPAI Hep C v2.0. Q6 - Hepatitis C effect on ability to perform normal daily activities, excluding job
- Similar to table 3.6.1.1, the following table will be constructed:
- Table 3.8.7 WPAI Hep C v2.0. Absenteeism (percentage of work time missed due to hepatitis C). Descriptive Statistics
    - Table 3.8.8 WPAI Hep C v2.0. Presenteeism (percentage of work time missed due to hepatitis C)
    - Table 3.8.9.A WPAI Hep C v2.0. TWP (percentage of overall work impairment due to hepatitis C)
    - Table 3.8.10 WPAI Hep C v2.0. TAI (percentage of general/non-work activity impairment due to hepatitis C)

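### SAP section 10.2 drops the bracket from the WPAI total work productivity (TWP) formula, so its presenteeism term is 1/100 of the intended size

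*SAP*

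**What the plan says.** Protocol section 9.7.5 defines the score with 100 outside a bracket that encloses both terms: "TWP: $100 * \{Q2/(Q2+Q4) + [Q4/(Q2+Q4)] * Q5/10" (the bracket closes after the last term). It puts all four WPAI scores on one scale, "the results of which will be presented as percentage of impairment from 0 to 100".

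SAP section 10.2 defines the same score, "TWP (percentage of overall work impairment due to hepatitis C", as "100 \times \frac{Q_2}{Q_2+Q_4} + \frac{Q_4}{Q_2+Q_4} \times \frac{Q_5}{10", with no bracket around the sum. The same section states that "WPAI outcomes are expressed as impairment percentages, with higher numbers indicating greater impairment and less productivity, i.e. worse outcomes", and it scales absenteeism, presenteeism and total activity impairment (TAI) by 100 correctly. It also refers to the WPAI:SHP v2.0 scoring manual.

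SAP section 16 declares no change to TWP: "The analyses methods in this SAP is fully consistent with the clinical study Protocol". The only departure it names is the dropped PSP regression.

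**The concern.** Under ordinary operator precedence the SAP formula adds a term on a 0–100 scale to a term on a 0–1 scale. TWP is the one WPAI score that combines time lost from work with impairment while at work. As printed, it is little more than absenteeism.

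Work productivity is part of the research question and is secondary objective 5 (Protocol sections 8.1 and 8.2.2). If the line is programmed as it stands, SAP tables 3.8.9.A, 3.9.9.A and 3.10.9.A would be wrong for the core population, the target population and the core population with sufficient follow-up. These tables follow the layout of Table 3.6.1.1, which also reports change from baseline, so the apparent effect of treatment on work impairment would be wrong too.

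**Working it through.** **Inputs.** Q2 is hours missed because of hepatitis C, Q4 is hours worked, and Q5 is the 0–10 rating of impairment while working (Protocol section 9.7.5; SAP section 10.2). The answer values below are illustrative, because the documents give no data. Neither document contains a worked TWP value to reproduce, so the two formulas are compared directly.

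**Notation.** Let a = Q2/(Q2+Q4), so that Q4/(Q2+Q4) = 1 − a, and let p = Q5/10.

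- Protocol: TWP = 100 × [a + (1 − a)p]
- SAP as printed: TWP = 100a + (1 − a)p

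**Ratio of the presenteeism terms.** (1 − a)p divided by 100(1 − a)p is 1/100 wherever the term is not zero.

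**Shortfall.** Protocol minus SAP is 99(1 − a)p = 9.9 × Q5 × Q4/(Q2+Q4) percentage points. With Q2+Q4>0 it is zero only when Q5=0 or Q4=0. It is largest at Q2=0 and Q5=10, where it is 99.

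**Single time points.**

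| Q2, Q4, Q5 | Absenteeism | Presenteeism | TWP, protocol | TWP, SAP | Shortfall |
|---|---|---|---|---|---|
| 0, 40, 1 | 0 | 10 | 10 | 0.1 | 9.9 |
| 0, 40, 5 | 0 | 50 | 50 | 0.5 | 49.5 |
| 4, 36, 3 | 10 | 30 | 10 + 0.9×30 = 37 | 10 + 0.9×0.3 = 10.27 | 26.73 |
| 10, 30, 5 | 25 | 50 | 25 + 0.75×50 = 62.5 | 25 + 0.75×0.5 = 25.375 | 37.125 |
| 0, 40, 10 | 0 | 100 | 100 | 1 | 99 |

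**Change from baseline.**

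- (0, 40, 5) to (0, 40, 2): protocol 20 − 50 = −30 points; SAP 0.2 − 0.5 = −0.3 points.
- (0, 40, 6) to (4, 36, 1): protocol 19 − 60 = −41 points; SAP 10.09 − 0.6 = +9.49 points. An improvement is reported as a worsening.

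**Internal consistency.** The protocol formula can be written as 100 × [p + a(1 − p)], so it is never below presenteeism, and by the same argument never below absenteeism. The SAP formula breaks this. A patient with Q2=0 and Q4>0 scores 100 × 0 + p, which cannot exceed 1%. On a grid of Q2 from 0 to 40 and Q4 from 2 to 60 in steps of 2 hours, with Q5 from 0 to 10 (21 × 30 × 11 = 6,930 combinations), the SAP value falls below the patient's own presenteeism score in 4,022. The protocol value does so in none. The grid shows how readily the inconsistency arises; it does not estimate the share of patients.

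**The case against.** The strongest reply is that this is a typographical slip with little practical consequence. Section 10.2 points to the scoring manual and calls the outcomes percentages, section 16 claims agreement with the protocol, and the protocol prints the bracket. A programmer who follows those would not code the line literally. If one did, a TWP of at most 1% beside a presenteeism of 50% would be conspicuous. TWP is one of four scores from a secondary questionnaire, no test is planned on it, and the sign reversal above is a constructed case of unknown frequency.

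Much of that stands as a limit on the consequence. It does not rescue the formula. A reader of section 10.2 has an explicit equation that contradicts the scale stated around it, and the equation is what gets programmed. The scoring manual is not among the documents and cannot settle the matter here; the protocol formula and the SAP's own percentage scale can.

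Two further reservations are fair. The SAP text was machine-read from a PDF, so a bracket lost in conversion cannot be wholly excluded. It is unlikely, because the protocol's bracket and the other three SAP formulas came through intact, and a look at the source PDF would settle it. The SAP also cites protocol version 4.0, whereas the protocol available is version 3.0. The contradiction within section 10.2 does not depend on the protocol version.

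**Conclusion.** The concern holds: the SAP formula for TWP is wrong as written and must be corrected. The presenteeism term is 1/100 of its intended size, and the score is too low by 9.9 × Q5 × Q4/(Q2+Q4) points, between 0 and 99, for every employed patient with Q4>0 and Q5>0.

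This rests on reading the formula as printed, with ordinary operator precedence. Results are affected only if it is programmed that way. The number of patients affected is unknown. SVR12, absenteeism, presenteeism and TAI are not affected.

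**What to change.** In SAP section 10.2, restore the bracket so that 100 multiplies the whole sum, as in Protocol section 9.7.5: TWP = 100 × {Q2/(Q2+Q4) + [Q4/(Q2+Q4)] × Q5/10}. Make the same correction in the program if the printed line has been coded.

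Add two program checks, both for patients with Q4>0 and the items present:

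- TWP equals presenteeism when Q2=0.
- TWP is never below presenteeism or absenteeism.

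A minor clarification can be made at the same time. When Q4=0 the questionnaire skips Q5, so the SAP should say whether Q5 counts as a needed item for TWP when Q2>0, where its weight in the formula is zero. When Q2 and Q4 are both zero the ratio is undefined, and the SAP should say that TWP is missing.

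The cost is one line in the SAP, one line in the program and two checks, with no new data. SAP section 2 allows revisions before database soft lock; after that, the correction would be explained in the study report.
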